PROTOCOL: Neurobiological and Psychological Benefits of Exercise in

Chronic Pain & PTSD

NCT#- 03283163

(1). Rationale:

(a). Statement of the Problem.

The wars in Iraq and Afghanistan are creating a new generation of Veterans, including an increasing number of women Veterans, who present with comorbid PTSD and chronic pain conditions from recent deployment-related physical injuries and exposure to psychological trauma. Health behavior change has become increasingly important in treating these conditions and proactively preventing long-term negative health sequelae, in order to benefit these Veterans directly and reduce the growing challenges to our healthcare system. The proposed CDA-2 program of research will use an innovative translational research approach to study whether a chronic progressive -based exercise program will reduce chronic pain in patients with PTSD and to elucidate and modify potential PTSD-related deficiencies in neurobiological and psychological responses to exercise to optimize the physical and psychological benefits of exercise for these individuals.

(b). Hypotheses or Key Questions.

The overall aims and hypotheses of the current protocol are:

Aim 1: Assess the degree of clinical change in chronic pain and PTSD symptoms between the screening session, baseline and endpoint assessment time-points across a 12-week progressive exercise training program.

Hypothesis 1: As compared to the screening evaluation and baseline exercise assessment, as a result of the progressive exercise training regimen, participants will experience clinically significant reductions in pain related symptoms as well as improvements in symptoms of PTSD by the endpoint exercise assessment (between week 13-15).

Aim 2: Compare the impact of the exercise training program on plasma levels of the anti-stress neuromodulator, allopregnanolone plus pregnanolone (ALLO +PA), among trauma-exposed participants with comorbid chronic pain and vary degree of PTSD symptom severity (CP/PTSD).

Hypothesis2a: At the baseline exercise assessment, ALLO +PA will be lower and increase less in response to the maximum load exercise than during the endpoint exercise assessment (week 13).

Aim 3: Determine whether maximum load exercise-induced increases in plasma ALLO+PA correlate with changes in pain symptoms as measured by the cold pressor test and self-reported pain ratings.

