Hypothesis 3a: At the baseline exercise assessment, diminished acute (maximum load) exercise-induced increases in ALLO+PA will be

associated with lesser acute exercise-induced decreases in pain sensitivity and lesser increases in tolerance as measured by the cold pressor test.

Hypothesis 3b: At the endpoint exercise assessment at the end of the progressive, intense exercise training regimen, MAX-EX-induced increases in plasma ALLO+PA will correlate with increases in pain tolerance/decreases in pain sensitivity when compared to baseline pre-training responses.

Exploratory Aim 1: Assess the role of exercise motivation and self-efficacy in relation ALLO+PA responses to exercise at the screening, baseline and endpoint exercise assessments.

Hypothesis: Participants with higher acute exercise-induced increases in ALLO+PA will show significantly higher levels of intrinsic motivation and self-efficacy for exercise, as well as lower levels of pain sensitivity (tolerance and threshold), pain-related symptoms and PTSD severity. Increases in intrinsic motivation will parallel increases in acute exercise-induced increases in ALLO +PA as the participant's progress through the 12-week chronic exercise training regimen.

(c) Specific Objectives.

Our main objective is to first determine if there are clinical, antinociceptive and anti-stress benefits of exercise for the trauma-exposed, chronic pain/PTSD population. Our second objective is to begin to delineate the interrelated pathophysiology of chronic pain and PTSD through our investigation of neurobiological factors such as ALLO+PA. These findings would ultimately inform development of more effective therapeutic interventions for these commonly comorbid conditions. For example, data from this pilot work will be used to compute effect sizes in support of a future clinical trial incorporating individually prescribed exercise regimens and a motivationally based exercise behavior change intervention aimed at reducing pain and PTSD symptoms in our Veterans. Specifically, this CDA-2 will allow the PI to develop a more effective, motivationally based, exercise behavior change protocol that fosters long-term exercise compliance in patients with chronic pain/PTSD which will be used as an adjunct to cognitive interventions for these disorders to be further developed and studied via a larger VA, NIH, or DOD-funded grant for which the PI will apply in years 4-5 of the CDA2.

2. Background and Significance

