PTSD Checklist (PCL-5)⁵²: The PCL is a 20-item self-report questionnaire designed to assess PTSD symptomatology. Participants are presented with a list of symptoms of PTSD and asked to indicate the extent to which they have been bothered by each of the symptoms during the past month using a 5-point Likert-type scale. While the psychometrics of the current version of the PCL is in the process of undergoing validation, the previous version of the PCL has been found to be internally consistent and reliable over time and therefore appears to be a valid measure of PTSD. In addition, this previous version has good sensitivity (.82) and specificity (.83).

Chronic Pain Measures

Pain/Pain Sensitivity/Tolerance Cold Pressor Test⁵³⁻⁵⁴: A procedure that has been used widely in laboratory studies to measure pain perception and tolerance⁷³.

To be administered at: Pre Exercise Testing sessions (Cold Pressor Assessment Sessions) & Post Exercise Testing at both exercise test sessions & Midpoint Self-Report Assessment Session

West Haven Yale Multidimensional Pain Inventory⁵⁵: The WHYMPI has been demonstrated to be applicable across a variety of clinical pain conditions. Its brevity, validity/ reliability, self-report nature and ease of scoring make it ideal for both clinical and research purposes. The WHYMPI is sensitive to change following rehabilitation. Please note only the interference subscale of the WHYMPI will be administered in this study.

To be administered at: Screening, Cold Pressor and Exercise Assessment Sessions & Midpoint Self-Report Assessment Session

McGill Pain Questionnaire: Short-Form⁵⁶⁻⁵⁷: The McGill short-form questionnaire consists of 15 descriptors (11 sensory, 4 affective) rated on an intensity scale of 0 to 3. This measure has been demonstrated to be a highly reliable measure of pain. Test-retest correlations have been found to range from 0.89-0.96

To be administered at: Screening, Cold Pressor (baseline and post cold pressor) and Exercise Assessment Sessions (baseline, post exercise and post cold pressor) & Midpoint Self-Report Assessment Session

Numerical rating scale: (NRS)⁵⁸. **NRS-I**, an 11-point numeric rating scale where a score of “0” represents no pain and a score of “10” represents the worst pain imaginable. Participants will be asked to rate their average pain over the past week. According to (Jensen, Turner, Romano & Fisher, 1999), this measure has psychometric properties sufficient for use in clinical research.

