To be administered at: Screening, Cold Pressor (baseline and post cold pressor) and Exercise Assessment Sessions (baseline, post exercise and post cold pressor), & Midpoint Self-Report Assessment Session

Pain Catastrophizing Scale: All 13 items on the PCS were drawn from previous experimental and clinical research on catastrophic thinking in relation to pain experience (Chaves and Brown, 1987; Rosenstiel and Keefe, 1983; Spanos et al., 1979). Factor analyses of the PCS have shown that catastrophizing can be viewed as a multidimensional construct comprising elements of rumination (“I can’t stop thinking about how much it hurts”), magnification (“I worry that something serious may happen”), and helplessness (“There is nothing I can do to reduce the intensity of the pain”). The factor structure of the PCS has been replicated in several investigations (Osman et al., 1997,2000; Sullivan et al., 1995, 2000; Van Damme et al., 2002).

To be administered at: Screening, Cold Pressor and Exercise Assessment Sessions & Midpoint Self-Report Assessment Session

Exercise Behavior and Motivation Measures

Godin Leisure-time Exercise Questionnaire⁵⁹ (The individual is asked to complete a self-explanatory, brief four-item query of usual leisure-time exercise habits. The participant indicates the frequency, intensity and duration of their exercise behaviors. Reliability estimates range from .83-.85.

To be administered at: Screening, Cold Pressor and Exercise Assessment Sessions & Midpoint Self-Report Assessment Session

Tampa Scale of Kinesiophobia⁶⁰⁻⁶¹: The Tampa Scale of Kinesiophobia is a 17-item self-report checklist developed as a tool to assess fear of movement or re-injury. It has two subscales, activity avoidance and somatic focus. The TSK demonstrates good construct and predictive validity (Roelofs et al, 2004). The total score ranges between 17 and 68, with higher scores representing a higher degree of kinesiophobia and a cut score of 37 or above considered to be a high score.

To be administered at: Baseline & Endpoint testing session (post-exercise testing) and Midpoint Self-Report Assessment Session

Transtheoretical Model of Exercise Stage of Change⁶²: A 23-item continuous measure designed to categorize individuals in one of five stages of change (precontemplation, contemplation, preparation, action and maintenance).

To be administered at: Screening, Cold Pressor Assessment Sessions & Midpoint Self-Report Assessment Session

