Cold Pressor Test (CPT): Measures of pain sensitivity will be obtained using the CPT, a procedure that has been used widely in laboratory studies to measure pain perception and tolerance,⁷⁰ as well as self-report measures of pain severity and disability and exercise motivation (Appendix 1). The cold pressor protocol will follow guidelines from a previously published study investigating similar variables.⁷⁰ Chronic pain mentor [name], who has experience administering the cold pressor test, will provide supervision. Participants will be instructed to hold their right hand in temperature-controlled ice water, inside a cold pressor apparatus, up to their wrist and to keep the hand still. They will be instructed to say when they first experience pain and will be told to withdraw their hand when the pain becomes intolerable. Therefore two measures of pain sensitivity will be derived: "pain threshold" and "pain tolerance". Pain threshold is defined as the number of seconds between hand immersion in the ice water and the first report of "pain." Pain tolerance is defined as the number of seconds between hand immersion and hand withdrawal from the water. A maximum seven-minute time limit for immersion, unknown to the patient, will be imposed. The CPT will be obtained: A) in relation to the acute maximum load exercise assessment (pre- and post-CPX), and B) in relation to progressive exercise training (before, at mid-point, and after completion).

A) Participants will perform baseline pain ratings and the CPT in the late morning **one to five days before** each CPX, two and a half hours after IV placement and the breakfast of power bars provided. Blood will be sampled from the IV for ALLO+PA measurement just prior to the pain ratings and CPT. Participants will have fasted since midnight, as per procedures for the CPX. The post-CPX pain ratings and CPT will be performed on the day of the CPX, immediately after the 30' post-CPX blood drawing for ALLO+PA. Obtaining the baseline and post-CPX pain assessments at the same time of day on two separate days will control for potential effects of diurnal variation on pain sensitivity, as well as ALLO+PA levels.

B) The procedures in A will be completed before and after completion of the chronic exercise training program.

C) In addition, the baseline pain ratings and CPT procedures in A will be performed at the mid-point of the progressive exercise training program.

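### The pain NRS asks for a past-week average but is repeated around the exercise test, so as worded it cannot serve as an acute pain outcome for Aim 3

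*Combined protocol and SAP*

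**What the plan says.** In the protocol's Chronic Pain Measures, the NRS is "an 11-point numeric rating scale where a score of “0” represents no pain" and 10 the worst imaginable. Its instruction is: "Participants will be asked to rate their average pain over the past week". The administration line beneath it lists screening, the cold pressor sessions (before and after the test) and "Exercise Assessment Sessions (baseline, post exercise and post cold pressor), & Midpoint Self-Report Assessment Session".

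Aim 3 asks whether the rise in ALLO+PA induced by maximum load exercise will "correlate with changes in pain symptoms as measured by the cold pressor test and self-reported pain ratings". Hypothesis 3a is narrower: a smaller ALLO+PA rise is expected to be "associated with lesser acute exercise-induced decreases in pain sensitivity and lesser increases in tolerance as measured by the cold pressor test". Hypothesis 3b also concerns pain tolerance and sensitivity.

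The Cold Pressor Test section, item A, fixes when ratings are taken around the exercise test: "Participants will perform baseline pain ratings and the CPT in the late morning", one to five days before each exercise test. For the second reading, "The post-CPX pain ratings and CPT will be performed on the day of the CPX", straight after the 30-minute blood sample. The stated reason for matching the time of day is to control diurnal variation.

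Under Data Analyses, Aims 2 and 3, the planned correlations use tolerance and threshold. Pain intensity appears only as one outcome of an exploratory regression, and no instrument is named for it.

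**The concern.** Repeating a pain rating around a stimulus is useful only if the rating can move on the time scale of that stimulus. A seven-day average is almost entirely fixed before the participant mounts the bicycle. Any difference between readings taken the same morning would be rating noise, or would come from participants answering about current pain instead of the question asked.

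Elsewhere the battery follows the expected pattern. The past-month PCL-5 and the BDI are given before exercise only. The POMS is given before and after, and is justified by its response to acute manipulations. The NRS joins a recall-period wording to an acute schedule.

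What is at stake is the NRS contribution to the self-report part of Aim 3. Current pain that was not asked about at the session cannot be recovered in analysis. The Specific Objectives say that this pilot will supply effect sizes for a future trial. A near-zero acute effect produced by item wording would be a poor basis for that.

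**Working it through.** The plan gives no figure of its own to reproduce here. The check is how far an acute change can move a seven-day mean.

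**Inputs**
- Recall window: 7 days = 168 hours = 10,080 minutes (NRS instruction).
- Smallest recordable change: 1 point (11-point scale).
- Duration of the acute change: 60 minutes (assumed), or 165 minutes from breakfast to the post-test rating. The 165 minutes is 120 (breakfast two hours before exercise, CPX section) + about 15 (target exercise time, CPX section) + 30 (delay to the post-exercise sample, Cold Pressor Test section).
- Longest plausible within-session duration: about 4.5 hours (session length in the consent information).
- Size of the acute change: not given in the documents; 3 points assumed, with 5 points as a larger case.

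**Formula.** Shift in the seven-day mean = acute change × duration / window length.

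| Acute change | Duration | Shift in seven-day mean |
|---|---|---|
| 3 points | 60 min | 3 × 60 / 10,080 = 0.018 |
| 3 points | 165 min | 3 × 165 / 10,080 = 0.049 |
| 5 points | 4.5 h | 5 × 4.5 / 168 = 0.13 |

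Turned round, a 1-point shift from a 4.5-hour window needs an acute change of 168 / 4.5 = 37 points on a 10-point scale. The conclusion therefore does not depend on the assumed effect size.

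**Using the earlier cold pressor session as baseline.** Two seven-day windows taken *d* days apart share (7 − *d*)/7 of their days.
- *d* = 1: 6/7 = 86%.
- *d* = 5: 2/7 = 29%.

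The days not shared contain ordinary daily pain, and the exercise bout is only a small part of them. A difference in the past-week NRS between these sessions mostly reflects those intervening days, so the earlier baseline does not rescue the item as worded.

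**The case against.** A reader might infer that the whole self-report half of Aim 3 is certain to be null, or that Aim 3 has lost its acute pain outcome. The documents do not support either reading, for these reasons.

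- **There is a second repeated rating.** The short-form McGill is given at the same pre/post points, with descriptors scored 0 to 3 for intensity and no recall period stated. Aim 3 and the Cold Pressor Test section speak of pain ratings without naming an instrument. The McGill may be able to register acute change; the text does not settle it.
- **The confirmatory parts of Aim 3 do not use the NRS.** Hypothesis 3a names the cold pressor test, Hypothesis 3b concerns tolerance and sensitivity, and the planned correlations use threshold and tolerance.
- **Intensity is not identified.** The regression is exploratory. The plan does not say that intensity means the NRS, or that the outcome is within-session change. A level, or a change from baseline to endpoint some 12 weeks later, could be measured with a past-week item.
- **A null is not guaranteed.** It follows only if every participant answers as worded. If some rate current pain, the scores mix two quantities; that is also uninterpretable, but it is a different failure.
- **Table 2 and the questionnaire forms were not in the text available.** A separate current-pain instruction there cannot be excluded. If one exists, it conflicts with the NRS description and still needs reconciling.

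All five points stand and limit how far the concern reaches. None of them makes a past-week average able to show an acute change, and nothing in the available text gives a current-pain version of the NRS.

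**Conclusion.** The concern holds for the NRS specifically. As worded and scheduled, it cannot act as an acute self-reported pain rating for Aim 3, or as an acute intensity outcome in the exploratory regression. Realistic acute changes alter the quantity it asks for by a few hundredths of a point. This rests on participants following the stated recall period, and on no different instruction appearing in Table 2 or on the forms.

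The cold pressor outcomes and the analyses built on them are unaffected. For Aim 1, where the interval is the training programme, a past-week average is a suitable measure. Whether the McGill fills the acute gap depends on an instruction that the plan does not state.

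**What to change.** 1. Keep the past-week NRS once per visit, before any exercise or cold pressor test, for Aim 1.
2. At every pre/post reading, use the same 0 to 10 item worded as pain right now, and give the McGill a present-pain instruction. Include the baseline ratings at the cold pressor session one to five days before the exercise test.
3. In Data Analyses, Aims 2 and 3, name the instrument that supplies intensity and the baseline that defines its change. The main baseline should be the cold pressor session reading, because the plan matches its time of day to the post-exercise reading. The same-session pre-exercise reading can be supporting. Using the same-session change alone would drop the diurnal control that the protocol sets up.
4. Check Table 2 and the forms against the new wording.

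The cost is one added item wording, an instruction on an existing form, a short addition to the analysis plan and an IRB amendment. No visit or procedure is added. The downside is that acute readings already taken with the past-week wording cannot be pooled for Aim 3.

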Inclusion Criteria: Only participants in whom a physical examination, medical history, EKG, and baseline laboratory studies including urine toxicology screens indicate that the symptoms limited cardiopulmonary exercise stress ((MAX-EX) testing will be safe will be included in this study. Also, participants will be required to start at a relatively sedentary level, defined as performing less than 30 minutes/day (150 minutes per week) of moderate physical activity on ≥ 5 days per week.⁸² Participants must be free of medications and other substances (e.g., illicit drugs and alcohol) with effects that could hinder data interpretation for 2-6 weeks depending on the medication and frequency of use (which must be cleared by the PI's primary mentor). However, psychotropic medications are allowed as long as the participant has been stable on them for two months. Those who are using tobacco will still be included in the study and will not be required to lower or stop their dosage/intake. If on pain medications with short half-lives,

participants must be off of them for 5 half-lives before testing, generally about 24 hours. Any participant with an ICD-9 or ICD-10 chronic pain diagnosis with a musculoskeletal etiology, as confirmed by the rehab medicine doctor or other qualified pain psychology staff, will be allowed for inclusion in the study. Any participant with a confirmed psychiatric diagnosis of PTSD, including those who are sub-threshold PTSD, or with trauma exposure without a diagnosis of PTSD, other psychiatric conditions, or chronic pain will be included in the study. Individuals in the PTSD group must meet for current chronic PTSD (≥ 3 months) or sub-threshold PTSD as assessed by the CAPS -5, 1-Month Diagnostic Version. Sub-threshold PTSD is determined using the CAPS-5. If a patient endorses 2 or 3 B-E criteria or all B-E criteria without functional impairment – with functional impairment defined as having clinically significant symptoms that interfere with daily activities. Subjects with chronic pain For individuals eligible for the polytrauma group (chronic pain, PTSD and mild and moderate TBI), any participant with a mild or moderate TBI (six months or longer post injury), as determined by the BAT-L will be included.

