Screening Evaluation for Study Eligibility: If considered potentially eligible and interested, participants will be invited for an in-person screening session in which they will first complete the informed consent process, according to the guidelines established by the Institutional Review Board (IRB) at the VABHS. After providing informed consent, the subject will answer assessment questionnaires and receive a physical examination, laboratory blood tests, a urinalysis, a urine toxicology test for illicit drugs, and an EKG. In addition to the initial qualitative "yes/no" test for tobacco use, we will test participants' urine cotinine level using Nymox NicAlert semi-quantitative test strips. Cotinine is the principal metabolite of nicotine and has a longer half-life (18 hrs vs. 2 hrs), and thus can be reliably used to estimate daily intake of nicotine. Cotinine tests will detect any tobacco use for the past few days, and therefore will be sensitive enough to test for any recent tobacco use when participants present for exercise assessment sessions. Although we will not be excluding tobacco users from the study, any level of tobacco use can impact accurate measurement of the antistress and antinociceptive neurohormones under investigation, therefore it is imperative that we are able to capture the level of cotinine for the participants who smoke and verify the non-smoking status of participants who identify as non-smokers. Finally, women will receive a urine pregnancy test at all in person study visits. The physical screening will be performed by [name] or her medical fellows.

**** Parts of the physical examination, lab tests, or the EKG and psychiatric assessments may be repeated in order to clarify results, or to track or evaluate possible medical/psychiatric problems during the study. To do this, the participant may be asked to return for an extra visit for which he/she will be compensated.**

****If a month or more of time lapses between the screening session and the baseline cold pressor assessment sessions, we will repeat the CAPS-5 to re-determine PTSD status, prior to any study procedures with the exception of the urine testing. Regardless of the outcome of the assessment, the participant will be compensated for the full amount of the cold pressor session.**

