Cardiopulmonary Exercise Test (CPX): All participants will complete a MAX-EX test within one to five days of the cold pressor test session (see below under Cold Pressor Test Session). During each test, we will be using rigorous means to control for the many confounders that potentially impact baseline NPY and ALLO levels as well as the pattern of neurotransmitters, peptides, and steroids released in response to exercise. Once eligibility is confirmed, the participant will present as scheduled, for the exercise testing session at the Clinical Studies Unit (CSU) and the entire session will take place between 8am and 12pm. In addition to our stringent, inclusion/exclusion criteria, participants will have been instructed to abstain from food and beverages, except for water, after midnight the evening before and to abstain from breakfast at home on the day of the testing procedure. Upon arrival at VABHS, the subject will be given water and power bars (6 kcal/kg) to provide the same baseline caloric load for all participants. The “breakfast” will be provided two hours before exercise, so that feeding-induced increases in ACTH, cortisol, glucose and other reactants will have returned to baseline before the first baseline blood sample is taken. During this time, they will also be completing self-report questionnaires (see Table 2). The MAX-EX testing will be performed in accordance with guidelines published by the American College of Cardiology.⁶⁹ Participants will sit in a comfortable chair for 60 minutes prior to testing. A catheter will be placed in a large superficial vein of the left arm. Once ready for exercise testing, the participant will be transported to the exercise testing room via wheelchair. The participant will then be shifted onto the upright testing bicycle and electrocardiogram electrodes will be applied at least 15 minutes prior to testing. During the MAX-EX, oxygen consumption (peak VO_2) and ventilatory anaerobic threshold (VAT),

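### Test-morning nicotine is neither standardised nor recorded, and cotinine cannot show it in regular smokers (minor)

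*Combined protocol and SAP*

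**What the plan says.** The Inclusion Criteria admit smokers without any test-day exception: "Those who are using tobacco will still be included in the study and will not be required to lower or stop their dosage/intake".

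Screening Evaluation for Study Eligibility explains why tobacco still matters: "any level of tobacco use can impact accurate measurement of the antistress and antinociceptive neurohormones under investigation". The chosen tool, added to a yes/no tobacco test, is the "urine cotinine level using Nymox NicAlert semi-quantitative test strips". The section gives three uses for it: estimating daily nicotine intake, verifying self-declared non-smokers, and picking up recent use when people attend exercise sessions. On the last it says: "Cotinine tests will detect any tobacco use for the past few days".

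The Cardiopulmonary Exercise Test section promises "rigorous means to control for the many confounders that potentially impact baseline NPY and ALLO levels". The controls it lists are a morning time window, a standard calorie load two hours before exercise, seated rest, and participants being "instructed to abstain from food and beverages, except for water, after midnight the evening before". The Cold Pressor Test section repeats the fast, places the resting test two and a half hours after IV placement and breakfast, and matches time of day between the resting and post-exercise tests. Neither section mentions tobacco or nicotine. The Data Analyses section names no tobacco or cotinine term.

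**The concern.** The outcomes are values on particular mornings, compared within a person. Pain threshold and tolerance are taken on a rest day and again after exercise one to five days later, and ALLO+PA is compared between the baseline and endpoint assessments. The relevant exposure is therefore nicotine on board that morning, whereas cotinine reflects intake over the preceding days. A smoker who smokes at 07:00 before one session and last smokes at 23:00 before the next has a different acute exposure at each. Nothing the plan records would reveal the difference.

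At stake is extra within-person variation in a pilot that needs 25 completers and analyses Aims 2 and 3 by simple correlations of change scores. Time of last use cannot be recovered reliably once the session is over.

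**Working it through.** **Inputs from the protocol.** Half-lives of 2 h (nicotine) and 18 h (cotinine), from the Screening Evaluation section. Time on site of about 2 h before exercise and 2.5 h before the resting cold pressor test.

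**Assumptions.** First-order decay. Equal cigarettes evenly spaced from 07:00 to 23:00 every day, at 10 to 30 a day. On the test day there is either one cigarette at 07:00 or none.

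**Check of the protocol's own inference.** The fraction of cotinine left after t hours is 2^(−t/18): 40% at 24 h, 16% at 48 h and 6% at 72 h. That agrees with detection over the past few days, so cotinine does suit the verification of non-smokers.

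**Effect of one morning cigarette.** Let B be the carry-over at 07:00, in cigarette units, from all earlier days:

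B = Σ 2^(−(31 − tᵢ)/h) / (1 − 2^(−24/h)), with tᵢ the clock hours of the day's cigarettes and h the half-life.

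The ratio of the level with the 07:00 cigarette to the level without it is 1 + 1/B. Both parts decay at the same rate, so the ratio stays constant through the morning.

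| Per day | Nicotine B | Nicotine ratio | Cotinine B | Cotinine rise |
|---|---|---|---|---|
| 10 | 0.136 | 8.4 | 9.13 | 11% |
| 15 | 0.191 | 6.2 | 13.7 | 7% |
| 20 | 0.246 | 5.1 | 18.2 | 5% |
| 30 | 0.358 | 3.8 | 27.3 | 4% |

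**Sensitivity to the assumptions.** Placing cigarettes at the midpoints of equal intervals over 16 waking hours gives nicotine ratios of about 10 (10 a day) and 5.5 (20 a day), with the same cotinine rises. Letting cotinine form gradually from nicotine lowers the rise at 2.5 h to about 6% (10 a day) and 3% (20 a day). In light users cotinine does move: 22% at 5 a day, 55% at 2 and 112% at 1.

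**Cotinine cannot date the last cigarette.** Yesterday's cigarettes were smoked 8 to 24 h before waking. Their average surviving cotinine fraction is (18/ln 2)/16 × (2^(−8/18) − 2^(−24/18)) = 1.623 × (0.735 − 0.397) = 0.549. One cigarette this morning therefore matches 1/0.549 ≈ 1.8 extra cigarettes yesterday.

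**Absolute size.** At 09:45 a 07:00 cigarette leaves 2^(−2.75/2) = 0.386 of its nicotine, against a carry-over of 0.052 (10 a day) to 0.095 (20 a day). At 10:45 it leaves 0.273. For a cigarette smoked just before arrival, 50% of the nicotine remains at 2 h and 42% at 2.5 h. The wait weakens the difference without removing it.

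**The case against.** The case against is substantial, and most of it limits the point.

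- **No effect on an outcome is shown.** The ratios describe nicotine, not ALLO+PA or cold pressor time. The protocol links tobacco to the neurohormones but gives no size and says nothing about timing. An effect on cold pressor pain is inference. This stands.
- **The contrast is extreme.** It sets a 07:00 cigarette against 8 hours without one. Moving the first cigarette from 06:00 to 07:00 changes nicotine at 09:45 only about 1.3-fold: (0.386 + 0.095)/(0.273 + 0.095) = 1.31 at 20 a day. A smoker with a fixed routine may have similar exposure every time. So exposure can differ; it need not.
- **Within-session ALLO+PA change is partly protected.** Samples before, during and up to 30 minutes after exercise share the same morning's smoking. The exposure to noise lies mainly in the two-day cold pressor contrast and in resting ALLO+PA compared across assessments. This stands.
- **Drift in smoking over 12 weeks.** A reader might infer that changing habits bias the baseline-to-endpoint comparison in a way cotinine cannot reveal. The documents do not support that. A change in daily intake is what cotinine measures; only a change in timing at constant intake stays hidden. That no cotinine term is planned is a separate gap.
- **Missing material.** Table 2 and any participant instruction sheets are not in the text reviewed, so a tobacco instruction there cannot be excluded. The strip's band limits are not given either, so whether it would register a 5 to 11% rise is unknown.

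None of this supplies a test-morning nicotine rule or a record of last use, so the gap remains.

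**Conclusion.** The point holds as a minor one. By the protocol's own account tobacco can disturb the measured hormones, yet preparation for the sessions leaves nicotine free. In people smoking about 10 or more a day, cotinine shows daily intake, not time of last use: one morning cigarette moves it 5 to 11% at 10 to 20 a day, while nicotine on board is about 5 to 8 times the overnight-abstinent level. The likely consequence is added noise, chiefly in the rest-day versus exercise-day cold pressor contrast and in resting ALLO+PA between baseline and endpoint.

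The conclusion rests on the stated half-lives, first-order decay and an assumed smoking pattern. The number of people concerned is unknown. If 20 to 30% of 25 completers used tobacco (an assumption), that would be 5 to 8 people who could be affected, not 5 to 8 who are. It would be wrong to conclude that Aims 2 and 3 are invalid or that ALLO+PA is distorted in proportion to nicotine; nothing in the documents quantifies either.

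**What to change.** In the Cardiopulmonary Exercise Test and Cold Pressor Test sections:

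1. Record the clock time of last tobacco or nicotine use on arrival at each of the five sessions (cold pressor at baseline, midpoint and endpoint; CPX at baseline and endpoint).
2. Ask users to keep their own usual interval before testing the same across sessions, with intake otherwise unchanged, as the Inclusion Criteria already provide.

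In the Data Analyses section:

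3. Add a sensitivity analysis that repeats Aims 2 and 3 without tobacco users whose interval differed between the compared sessions by more than a tolerance fixed in advance. Do not enter the interval as a covariate for the whole sample, because it is undefined for non-users.
4. Report cotinine at each session alongside, so that any change in daily intake is visible.

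The cost is one question per visit, one line in the preparation instructions, and a few flagged sessions. Excluding a flagged user also loses that person's pair from a small sample, which is why this belongs in a sensitivity analysis and not the main one.
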